4.2.3.3 Critical Structures

All OAR's listed in Table 2-4 should be contoured if there is any risk that the OAR constraints will be exceeded.

4.2.3.4 Primary Site (Primary Lung Lesion, Mediastinal/Hilar/SuprACLavicular Disease)

Radiation to the primary site can be delivered with 3D conformal therapy, IMRT, or PBT, at the discretion of the treating radiation oncologist. Standard simulation for treatment to the primary site involves immobilization with an upper body cradle and the arms over the head. The radiation dose to the primary site will be determined by the treating physician and based on normal tissue tolerance and institutional standards. Concurrent chemotherapy is permitted.

In addition, it is acceptable to utilize a simultaneous integrated or sequential boost to further increase dose to the CTV or GTV, at the physician's discretion.

4.2.3.5 Metastatic Sites

Radiation to the metastatic sites can be delivered with 2D/conventional techniques, 3D conformal therapy, IMRT, SRS, or PBT, at the discretion of the treating radiation oncologist. Radiation simulation is dependent on the site being treated, and immobilization devices include but are not limited to upper body cradles, stereotactic body cradles, lower body cradles, SRS immobilization, or a head and neck mass.

The radiation dose to metastatic sites will be determined by the treating physician and based on normal tissue tolerance and institutional standards.

4.2.3.6 Dose Calculation

Doses are to be calculated with CT based heterogeneity corrections, i.e. corrections are made for density differences between air spaces, lungs, water-density, or bone tissue.

5. Symptom Assessment during Protocol Treatment

A) As noted below in “Evaluation of Outcomes of Interest,” patients will be evaluated in the clinic for toxicity at follow-up visits every 8 +/- 2 weeks until 1 year, and then less frequently thereafter. Concordant with these clinic visits, the research team will capture toxicities in our toxicity log that meet the following criteria, per institutional policy: a) severe, defined as CTCAE v4.0 Grade 3 or higher, 2) unexpected, or 3) unanticipated. In addition, we will ensure that all relevant toxicities (severe, unexpected, or unanticipated) are documented appropriately in the medical record.

B) *Multiple-symptom assessment tool (optional)*. Symptoms will be measured by the Lung Cancer module of the MDASI²⁴. The MDASI is a multiple-symptom measure of cancer-related symptoms²⁵ that is sensitive to disease and treatment changes in lung cancer. This instrument is brief, easily understood, and validated in the lung cancer population. Patients rate the intensity of physical, affective, and cognitive symptoms on 0–10 numeric scales, ranging from “not present” to “as bad as you can imagine.” Patients also rate the amount of interference with daily activities caused by symptoms on 0–10 numeric scales, ranging from “did not interfere” to “interfered completely.” The MDASI-LC has 3 additional items known to be important in assessing patients with MM or MM therapies (constipation, coughing, sore throat). The MDASI-LC takes less than 5 minutes to complete. It can be completed at home using the web or an interactive voice response-computer system that calls the patient to have them rate their symptoms and symptom interference²⁶. Symptom severity and interference over time will be a secondary endpoint. The MDASI is included in Appendix C, and this data will be collected from each patient at each follow-up visit as described in the *Evaluation of Outcomes of Interest* section (every 6-8 weeks for the first year).

6. Optional Procedures after Induction Chemotherapy

A) Tissue specimen collection for biomarker analysis:

[figure not shown]
Diagnostic and surgically resected tumor tissue from lung and metastasis sites will be acquired from the source used to establish the diagnosis of malignancy, including archival specimens stored in the Pathology Departments and residual fresh or fixed tissues banked in institutional tissue banks. The tissue samples will include cytology and tissue samples. The samples to be collected will be archival smear slides, cell or tissue blocks, histology sections, and frozen tissue or cell specimens. The cell and tissue samples will be catalogued, reviewed by a pathologist for malignant cell content and pathological analyses, and for correlative molecular marker studies. The molecular marker analysis will include, among others, the analysis of protein expression, gene expression, copy number, mutation, and translocations, and micro-RNA expression abnormalities. The methodology to be used to examine molecular changes will be selected based on the characteristics of the sample collected (e.g., cells or tissue, archival or fresh frozen).

B) Serologies – Blood-based Biomarkers

Optional blood samples will be collected at baseline (e.g., at randomization), then every 8 weeks +/- 2 weeks while receiving treatment. If possible, these collections should also be timed to occur at the end of LCT, if applicable, and at the end of chemotherapy cycles 1, 2, and every 2 cycles thereafter. If on the immediate LCT arm, samples will be collected after LCT, then according to the schema above for the delayed/no LCT arm. Blood will be collected and either immediately analyzed or stored frozen until ready for analysis. Cells from blood, including circulating tumor cells (CTCs) will be quantitated and isolated by antibody-based capture methods using tumor antigens including Ep-CAM. Isolated cells will be assessed for markers from relevant pathways through analysis of DNA

(mutations, copy number variations, and single nucleotide polymorphisms (SNPs)), gene expression, and protein. Proteomic studies of circulating proteins including cytokines and angiogenic factors (CAFs) will also be conducted. Additional details of these analyses are provided in Appendix D and Appendix E.

Timeline for Blood Collection

Submit materials as follows:

For central review overnight directly to:
UTMD Anderson Cancer Center,
[name],
[name]
[name]
Lab [contact]

Blood and Tissue banking will be stored at:
CryoGene Lab
[name]
[name]
[name]

C) Quality of life multiple-symptom assessment pool- see section 5B above.

7. Statistical Considerations

7.1 Preliminaries. The purpose of this study is to test the hypothesis that the treatment paradigm of immediate LCT after induced oligometastatic disease can lead to reduced rates of disease progression. Patients will be randomized between immediate LCT and delayed/no LCT arms. The primary outcome will be progression-free survival (PFS) time, defined as the time from the time of randomization (immediate LCT vs. delayed/no LCT) to disease progression or death. The primary goal will be to compare the PFS times of these two arms.

7.2 Database Used for Collection. Study data will be collected and managed using REDCap (Research Electronic Data Capture) electronic data capture tools hosted at MD Anderson. [ref] REDCap (www.project-redcap.org) is a secure, web-based application with controlled access designed to support data capture for research studies, providing: 1) an intuitive interface for validated data entry; 2) audit trails for tracking data manipulation and export procedures; 3) automated export procedures for seamless downloads to common statistical packages; and 4) procedures for importing data from external sources. In the case of multi-center studies REDCap uses Data Access Groups (DAGs) to ensure that personnel at each institution are blinded to the data from other institutions. REDCap (<https://redcap.mdanderson.org>) is hosted on a secure server by MD Anderson Cancer Center's Department of Research Information

Systems & Technology Services. REDCap has undergone a Governance Risk & Compliance Assessment (05/14/14) by MD Anderson's Information Security Office and found to be compliant with HIPAA, Texas Administrative Codes 202-203, University of Texas Policy 165, federal regulations outlined in 21CFR Part 11, and UTMDACC Institutional Policy #ADM0335. Those having access to the data file include the study PI and research team personnel. All protected health information (PHI) will be removed from the data when it is exported from REDCap for analysis. All dates for a given patient will be shifted by a randomly generated number between 0 and 364, thus preserving the distance between dates. Dates for each patient will be shifted by a different randomly generated number. Following publication study data will be archived in REDCap.

7.3 Randomization. In lieu of stratification, the randomization will balance dynamically on five prognostic covariates related to PFS using the method of Pocock and Simon²⁷. The covariates are:

1) number of metastases (1 vs. 2-3), 2) response to first-line chemotherapy (SD vs. PR/CR), 3) CNS metastases (yes/no), 4) N0/N1 vs. N2/N3, and 5) EGFR/EML4ALK status. The randomization will be carried out using the Department of Biostatistics Clinical Trials Conduct Website.

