1.2 Secondary Objectives

The secondary objectives of this study will be to:

- Determine the overall survival
- Safety/tolerability of LCT
- Time to progression of prior metastatic lesions
- Time to appearance of new metastases (CNS vs. extra-CNS, treated lesion vs. new site)
- Quality of life

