4.2 Immediate LCT (local consolidation therapy) Arm

Patients who undergo LCT will have ablation of all residual local and metastatic sites of disease by surgery and/or radiation therapy. The optimal form of LCT will be determined by the treating physician(s). Consultation with a multidisciplinary group including a medical oncologist, thoracic surgeon and radiation therapist is encouraged. After the completion of LCT the patient will be treated with surveillance or maintenance treatment as determined by medical oncologist and described below.

4.2.1 Delayed/No LCT Arm – LCT given at the time of progression or toxicity after maintenance therapy or observation

Prior to treatment with maintenance therapy, we recommend adequate hematologic function as defined by an absolute neutrophil count (ANC) $\geq 1,500/\text{mm}^3$, platelet count $\geq 100,000/\text{mm}^3$, WBC $\geq 3,000/\text{mm}^3$, and hemoglobin $\geq 9 \text{ g/dL}$ within 3 weeks of study entry. We also recommend adequate hepatic function as defined by a total bilirubin level $\leq 1.5 \times$ the upper limit of normal (Serum bilirubin $\geq 1.5 \times$ Upper Limit of Normal in the setting of known Gilbert's disease is allowed), and alkaline phosphatase, AST and ALT $\leq 2.5 \times$ the upper limit of normal or $\leq 5.0 \times \text{ULN}$ if liver metastases are present.

Currently, there is no single standard maintenance approach and treatment is typically chosen based on clinical factors and tumor features (e.g., histology and mutation status). Patients randomized to this arm will receive maintenance therapy (switch or continuation), or surveillance, based on physician choice. Pemetrexed, bevacizumab, crizotinib (for ALK-mutation positive patients) or erlotinib are recommended as acceptable maintenance agents but other agents may be used at physician discretion.

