7.5 Statistical Analysis Plan

Descriptive statistics will be provided to summarize the patient characteristics and toxicities by the treatment arms (immediate LCT and delayed/no LCT groups). Chi-square test or Fisher's exact test will be applied to compare patient characteristics between the two arms. The balance of the five prognostic covariates (used in the Pocock-Simon's dynamic allocation method) between the two arms will be examined as well. For the primary endpoint, PFS, Kaplan-Meier estimate will be computed, and the log-rank test will be performed to compare the difference of PFS between the two arms. Cox regression model will be applied to correlate PFS with potential covariates in both the univariate and multi-covariate analyses. Patients are considered evaluable for efficacy if they receive at least one of the intended local consolidation therapy. Both the intent-to-treat analysis and analysis among the evaluable patients will be performed. The corresponding results will be compared and contrasted. For the secondary endpoints, similar analysis will be performed on the overall survival and other time-to-event endpoints. Safety and tolerability of the immediate LCT arm and delayed/no LCT arm will be summarized by descriptive statistics. Quality of life will be analyzed by the repeated measures analysis of variance to count for the change before and after treatment and during the follow-up period. Proper transformation will be performed if necessary to transform data to be closer to the Gaussian distribution. All the statistical analyses will be two-sided with a P-value of 0.10 or less considering statistically significant.

Note that the MDACC DSMB will be providing study-wide oversight in regards to the endpoints described above.

To account for patients that crossover for reasons other than RECIST progression of disease (e.g. toxicity, growth of the malignancy that does not constitute RECIST progression), censoring will occur at the time of crossover for our primary analysis. In addition, a secondary time varying covariate Cox model analysis will be done to assess the impact of crossover without RECIST progression.

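### Grade 1-2 toxicities are logged only if unexpected or unanticipated, with neither term defined, so a by-arm toxicity summary without a grade limit is incomplete below Grade 3 and may not be comparable between arms

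*Combined protocol and SAP*

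**What the plan says.** Section 1.2 lists "Safety/tolerability of LCT" among the secondary objectives.

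Section 5, item A, sets the collection rule. At follow-up visits, and under institutional policy, an event goes into the study's log only if it is "a) severe, defined as CTCAE v4.0 Grade 3 or higher, 2) unexpected, or 3) unanticipated". The sentence after it asks that "all relevant toxicities (severe, unexpected, or unanticipated) are documented appropriately in the medical record", so the instruction for the chart carries the same three categories as the log.

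Section 7.5 sets the use. "Descriptive statistics will be provided to summarize the patient characteristics and toxicities by the treatment arms", and later "Safety and tolerability of the immediate LCT arm and delayed/no LCT arm will be summarized by descriptive statistics". Neither sentence limits the summary to a grade, and neither names its data source.

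The arms receive different treatment. Under Section 4.2, "Patients who undergo LCT will have ablation of all residual local and metastatic sites of disease by surgery and/or radiation therapy", followed by surveillance or maintenance. In the delayed/no LCT arm (Section 4.2.1), "Patients randomized to this arm will receive maintenance therapy (switch or continuation), or surveillance, based on physician choice". Section 1.3 describes the study as open-label.

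**The concern.** A rule that logs severe and surprising events suits safety reporting. It suits a by-arm description of tolerability less well, because below Grade 3 an event enters the log only on a judgement about whether it was to be expected. The documents do not say against what that judgement is made.

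In its ordinary sense, expectedness is relative to the treatment given. A Grade 2 oesophagitis after chest radiotherapy may be thought expected and left out, while the same event in a control on surveillance may be thought unexpected and logged. Whoever makes the judgement can know the arm. What is at stake is the low-grade part of a stated secondary objective: a table that looks like all-grade toxicity by arm would hold only a selected part of the Grade 1-2 events, possibly selected differently in each arm. Later analysis cannot restore events that were never recorded.

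**Working it through.** **What the rule admits.** The plan states no safety figure to reproduce, so the first step is to set the rule against the use.

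| Event | Meets a logging criterion in Section 5A? | Inside the scope of the Section 7.5 summary? |
|---|---|---|
| Grade 3 or higher, either arm | Yes, whatever its expectedness | Yes |
| Grade 1-2, judged unexpected or unanticipated | Yes | Yes |
| Grade 1-2, judged expected | No | Yes, since no grade limit is stated |

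The third row is the gap. No other clinician-graded source fills it: the chart instruction repeats the filter, and Appendix A schedules toxicity assessments without widening what is logged.

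**Illustration of size.** Inputs from the plan: 94 randomised (Section 7.4), 1:1 (Section 4.0), so 94 / 2 = 47 per arm. The event rates and logging probabilities are assumptions. For one type of Grade 1-2 event, let p be the true rate and c the probability of logging, with L for LCT and C for control:

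- logged patients in an arm = 47 × p × c
- logged difference (LCT minus control) = pL × cL − pC × cC

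For an LCT-typical event, the entries are patients in the LCT arm against control, with the difference in percentage points:

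| True rates, LCT / control | All logged | cL = 0, cC = 1 | cL = 0.1, cC = 1 | cL = 0, cC = 0.5 | Expected in both (cL = cC = 0) |
|---|---|---|---|---|---|
| 30% / 5% | 14.1 v 2.4 (+25) | 0 v 2.4 (−5) | 1.4 v 2.4 (−2) | 0 v 1.2 (−2.5) | 0 v 0 (0) |
| 40% / 10% | 18.8 v 4.7 (+30) | 0 v 4.7 (−10) | 1.9 v 4.7 (−6) | 0 v 2.4 (−5) | 0 v 0 (0) |
| 50% / 10% | 23.5 v 4.7 (+40) | 0 v 4.7 (−10) | 2.4 v 4.7 (−5) | 0 v 2.4 (−5) | 0 v 0 (0) |
| 20% / 20% | 9.4 v 9.4 (0) | 0 v 9.4 (−20) | 0.9 v 9.4 (−18) | 0 v 4.7 (−10) | 0 v 0 (0) |

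Where the true rate is higher on LCT, the sign reverses only if cL / cC is below pC / pL. At 40% against 10% that threshold is 0.10 / 0.40 = 0.25; at 30% against 5% it is 0.05 / 0.30 = 0.17. A milder imbalance in logging shrinks the difference without reversing it.

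**Why the net direction is open.** Apply the same formula to a maintenance-drug effect, with assumed true rates of 10% on LCT and 40% in controls, logged in LCT patients on surveillance (cL = 1) and treated as expected in controls on the drug (cC = 0). The true difference is −30 points. The log shows 47 × 0.10 × 1 = 4.7 against 0, or +10 points, which now counts against LCT. Adding this to the 40% / 10% LCT-typical event under all-or-none logging gives logged totals of 0 + 4.7 = 4.7 against 4.7 + 0 = 4.7. If LCT patients also receive the drug, the effect can be dropped in both arms.

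**The case against.** The best defence is that the documents never tie expectedness to the arm. The criteria apply under an institutional policy that is not reproduced, and that policy may use one list for everybody. Logging would then be alike in both arms and no false difference would arise. This stands as a limit: differential capture is a possibility that the text leaves open, not a rule that it states. It does not answer the loss of expected low-grade events, which happens under any definition.

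A reader might go further and infer that all-grade totals would favour LCT, or that the direction would be reversed. The documents do not support that. Controls may receive maintenance drugs whose expected Grade 1-2 effects are equally unlogged, and LCT patients may receive them after LCT. Nor need LCT-typical effects be unexpected in controls: urgent local treatment is allowed before randomisation in either arm (Section 4.0), and controls may later receive LCT (Section 7.6). LCT may also be surgery, or radiotherapy outside the chest. A logged count of zero on LCT against full logging in controls is the extreme case.

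Two further points are fair. Section 7.5 does not name the log as its source, plans only description, and specifies no test for toxicity. And the MDASI-LC asks about cough, sore throat, shortness of breath, pain and fatigue whatever their expectedness, at the same scheduled visits as the toxicity assessment. It is optional, patient-reported and not CTCAE-graded, so it mitigates the gap only in part.

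**Conclusion.** The concern holds as one of incomplete and possibly non-comparable ascertainment below Grade 3. Followed as written, the plan drops expected Grade 1-2 effects in both arms and leaves undefined the judgement that decides which low-grade events remain. LCT-typical Grade 1-2 events can therefore be under-recorded in the LCT arm relative to controls.

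This rests on two readings: that expectedness may be judged against the treatment received, and that the log is the source for the Section 7.5 summaries, since no other clinician-graded source is described. The size cannot be taken from the documents. In the illustration, a true difference of +30 points could appear as anything from −10 to 0 under the logging patterns shown, and any reversal depends on the assumed rates and logging probabilities. The net direction across all low-grade events is not determined. Grade 3 or higher counts are not affected by this rule, and the primary PFS analysis is not touched. The point is worth correcting because tolerability is a stated objective and the correction is cheap.

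**What to change.** In Section 7.5, state that the by-arm toxicity comparison is restricted to Grade 3 or higher, and that logged lower-grade events will be listed separately without by-arm rates. State also that low-grade tolerability is then not compared by CTCAE grade, and that the optional MDASI-LC gives partial, patient-reported information on it. This costs one sentence or two; the price is having no by-arm low-grade rate.

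If low-grade tolerability is wanted, change Section 5A to record Grade 1-2 events, or one prespecified list of them, in both arms regardless of expectedness, at the visits already scheduled in Appendix A. A list must include the Grade 1 events of interest, or those remain lost. The cost is modest extra data entry, with no change to treatment, visits or sample size. Section 7.4 refers to the first 6 months of enrolment, so for any patients already followed under the present rule, expected low-grade events may not be recoverable, and the table should state from when the wider capture applies.

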7.4 Design

Design Assumptions:

Primary endpoint	Progression-free survival (PFS)
Null hypothesis	Median PFS equals to 4 months in both groups
Alternative hypothesis	Median PFS equals to 4 months in the delayed/no LCT group and equals to 7 months in the immediate LCT group.
Associated hazard ratio	0.57 = 75% improvement in median PFS
Type I error	10%
Type II error	10%
Accrual rate	2-3 patients/month
Follow-up	9 months

A design with one-sided 10% type I error and 90% power would require an expected number of progression events of 87 under the alternative hypothesis to detect 75% improvement in median PFS. Given these assumptions, this design would require 94 patients *randomized* over 37.6 months with additional 9 months of follow-up. One interim analysis will be performed to allow for the early termination of the trial in light of evidence that the LCT arm is superior to the no LCT arm or there is no difference between the two treatment arms. In order to provide an overall significance level of 0.05 for the study, the interim analysis will use a Lan-DeMets monitoring boundary with an O'Brien-Fleming stopping rule (East 5.4.2.0, Cytel 2011). The interim analysis will be performed when 44 out of the expected 87 events have been observed. Using O'Brien-Fleming test boundaries, the Z-score test cut-off at the interim analysis for stopping and rejecting the null hypothesis will be 2.054, the Z-score test cut-off at the interim analysis for stopping and rejecting the alternative (futility) is -0.203.

In order to obtain 94 patients for randomization, we estimate that 25% of patients (24) will undergo progression of disease during induction chemotherapy based on the first 6 months of patient enrollment. In addition, we anticipate that 20% of patients (19) will refuse randomization after up-front systemic therapy. Therefore, in order to randomize 94 patients, we anticipate that we will need to enroll $94 + 24 + 19 = 137$ patients. Note that patients who cross-over to the alternative treatment arm due to toxicity will be censored at the time of crossover, with the last progression-free date being the date of crossover.

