4.0 Treatment Plan

Prior to randomization, eligible patients will have received 4-6 cycles of induction chemotherapy, erlotinib or afatinib (for patients with known EGFR mutations) or crizotinib (for patients with known EML4-ALK fusion) without evidence of RECIST progression. They will be registered and then randomized in a 1:1 fashion to either immediate or no/delayed LCT. All patients will be followed until progression of disease is documented or two years after randomization, whichever comes first. Patients with metastases involving the brain or spinal cord, or metastatic lesions causing symptoms requiring palliation (e.g., bone, soft tissue) may be treated with surgery or radiotherapy prior to the completion of induction chemotherapy (randomization).

The following imaging studies are suggested after first-line therapy to assess the number of sites: 1) imaging of the brain with either a magnetic resonance imaging (MRI) scan (preferred) or a CT scan of the brain with contrast, and 2) systemic imaging with a positron emission tomography/computed tomography (PET/CT) scan or a CT scan of the chest/abdomen/pelvis with contrast. Other studies, such as a bone scan, and aspiration of pleural fluid, are at the treating physician's discretion.

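### The level of the primary PFS test is stated in three conflicting ways, and the printed interim boundary and 90% power fit only one-sided 0.10

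*Combined protocol and SAP*

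**What the plan says.** Three statements bear on the level of the primary PFS comparison.

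- Section 7.4, sample size: "A design with one-sided 10% type I error and 90% power would require an expected number of progression events of 87". The table in that section also lists type I error as 10%.
- Section 7.4, a few sentences later: "In order to provide an overall significance level of 0.05 for the study, the interim analysis will use a Lan-DeMets monitoring boundary", with an O'Brien-Fleming rule. Whether this 0.05 is one- or two-sided is not stated.
- Section 7.5, in the paragraph that names the log-rank test for PFS: "All the statistical analyses will be two-sided with a P-value of 0.10 or less considering statistically significant". No exception is made for the primary test.

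For the single interim look, at 44 of 87 events, Section 7.4 says that "the Z-score test cut-off at the interim analysis for stopping and rejecting the null hypothesis will be 2.054"; the futility cut-off is -0.203. No cut-off is printed for the final analysis.

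**The concern.** The success criterion for the primary endpoint depends on which sentence is followed. The design was powered at one-sided 0.10. Section 7.5 asks for a two-sided p of 0.10, which in the direction of benefit is one-sided 0.05. The sentence that introduces the boundary claims 0.05 overall.

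Two decisions are affected. At the interim, a monitoring board told that 2.054 protects an overall level of 0.05 could stop for superiority on evidence that does not meet that level. At the end, a result between the two thresholds could be called positive or negative, and the choice would be made after the data are known. The stated 90% power also belongs to only one of the readings.

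**Working it through.** **Inputs.** Section 7.4: "Median PFS equals to 4 months in the delayed/no LCT group and equals to 7 months in the immediate LCT group", so HR = 4/7 = 0.571 (the table prints 0.57) and ln(7/4) = 0.5596; 87 events; interim at 44 events; 94 patients, 37.6 months of accrual and 9 months of follow-up. Section 4.0: 1:1 allocation. Section 7.5: log-rank test.

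**1. Reproduce the plan's figures at one-sided 0.10.**

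- Events without an interim look (Schoenfeld): 4(z_α + z_β)² / (ln HR)² = 4(1.2816 + 1.2816)² / 0.5596² = 83.9.
- Lan-DeMets O'Brien-Fleming spending at information fraction t: 2[1 − Φ(z_{1−α/2}/√t)]. With α = 0.10 and t = 0.5: 2[1 − Φ(1.6449/0.7071)] = 0.0200, so the interim Z is 2.054, as printed.
- Adding beta spending of the same form (0.0200 at the interim) with non-binding futility gives 87.5 events. The drift is 0.5596 × √(87.5/4) = 2.617, and the futility bound is 2.617 × √0.5 − 2.054 = -0.203, as printed.
- The final critical value is Z = 1.316 (1.30 if futility is binding).
- Exponential PFS and uniform accrual give event probabilities of 0.968 (median 4 months) and 0.892 (median 7 months): 47 × (0.968 + 0.892) = 87.4 expected events.

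The design block is therefore internally consistent at one-sided 0.10. At exactly 44/87 the interim Z would be 2.039; that is rounding of t and does not matter here.

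**2. Ask what level 2.054 implies.** Inverting the spending function at t = 0.5 gives one-sided 0.0999. Other boundary families at one-sided 0.10 / 0.05 / 0.025 do not give 2.054: classical O'Brien-Fleming 1.899 / 2.373 / 2.797; Lan-DeMets Pocock 1.538 / 1.866 / 2.157; classical Pocock 1.527 / 1.875 / 2.178.

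**3. Repeat at each level.** Fixed-design power is Φ(0.5596 × √(87/4) − z_α) = Φ(2.610 − z_α). Power with the interim comes from two-look numerical integration.

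| Level | Interim Z (t = 0.5) | Final Z (non-binding) | Power, 87 events: fixed / with interim | Events for 90% power: fixed / with interim |
|---|---|---|---|---|
| One-sided 0.10 | 2.054 | 1.316 | 90.8% / about 90% | 84 / 87–88 |
| One-sided 0.05 (or two-sided 0.10) | 2.538 | 1.662 | 83.3% / about 83% | 110 / 112–113 |
| Two-sided 0.05 | 2.963 | 1.969 | 74.2% / about 74% | 135 / 136–138 |

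**4. Apply the printed rules literally.** Interim Z above 2.054, then two-sided p ≤ 0.10 at the end (Z = 1.645, not adjusted for the interim look), gives an overall one-sided alpha of 0.059 and power of 84%.

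**5. Translate to observed hazard ratios,** using HR ≈ exp(−2Z/√events).

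- Final, 87 events: Z = 1.32 is HR 0.75; Z = 1.645 is HR 0.70; Z = 1.969 is HR 0.66.
- Interim, 44 events: Z = 2.054 is HR 0.54; 2.538 is HR 0.47; 2.963 is HR 0.41.
- With both printed interim bounds applied, the chance of finishing between Z of about 1.32 and 1.645 is about 6% at HR 4/7, 11% at a true HR of 0.70 and 4% under the null.

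**The case against.** The best defence is that nothing was miscalculated. The events, patients, interim bounds and power agree with each other at one-sided 0.10, an acceptable choice for a phase II trial, and the final bound follows from the spending function even though it is not printed. On this view the 0.05 clause and the Section 7.5 sentence are stray wording. That is right about the sizing, and the finding does not challenge it. But the stray sentences are in force, and one of them is the only place where the plan puts a number on final significance.

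It can also be said that three statements need not mean three thresholds. If the 0.05 is one-sided, it matches two-sided 0.10 in the direction of benefit, leaving two. This stands as a qualification: the lower power is then about 83%, and 74% arises only if 0.05 is two-sided. Either way, power is below 90%.

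Finally, the alpha of 0.059 and power of 84% describe one literal reading, since a spending function would normally adjust the final bound. That is fair; they should be read as conditional on that reading, and the excess over 0.05 is small. The conflict does not rest on them.

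**Conclusion.** The concern holds. The plan states the level of its primary test in three ways, which amount to two or three different thresholds, and never says which governs. The interim boundary and the 90% power belong to one-sided 0.10 alone. At one-sided 0.05 or two-sided 0.10, power with 87 events is about 83%; at two-sided 0.05 it is about 74%. A final hazard ratio of about 0.70 to 0.75 is positive under the design and negative under Section 7.5; if 0.05 is two-sided, the disputed zone extends down to about 0.66. The figures assume proportional hazards, HR 4/7, 1:1 allocation and an interim at half information. This must be fixed, because it leaves the primary success criterion open and misdescribes the error control of an early-stopping rule.

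**What to change.** The sponsor should first declare one level and sidedness for the primary PFS test, before any look at unblinded data.

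- **If one-sided 0.10 was intended, as the printed figures indicate:** replace the 0.05 in Section 7.4 with an overall one-sided level of 0.10. Say whether futility is binding. Print the final boundary: Z about 1.32 (one-sided p about 0.094) if non-binding, or Z about 1.30 (p about 0.097) if binding, to be recomputed from the actual event fraction. Limit the two-sided 0.10 sentence in Section 7.5 to the other analyses. This costs wording only.
- **If 0.05 was intended:** state its sidedness. Replace the interim cut-off with about 2.52–2.54 (one-sided) or 2.94–2.96 (two-sided), re-derive the futility bound, print the final boundary and restate power as about 83% or 74%. This needs no extra patients if the lower power is accepted. Keeping 90% power would take about 112–113 or 136–138 events with the interim. Longer follow-up alone cannot supply these, because only 94 patients are to be randomized.
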